**5.0**                    **OBJECTIVES**

The study objective is to evaluate the efficacy and safety of hormone replacement therapy with matching doses of Armour Thyroid (ATH) in comparison to synthetic T4 in previously hypothyroid participants who are euthyroid on synthetic T4 replacement therapy (25-200 µg T4 daily).

In addition, this study will validate the dose-conversion table by evaluating a safe and effective dose conversion from synthetic T4 to Armour Thyroid in participants who are euthyroid on a stable dose of synthetic T4.

**6.0**

**POPULATIONS FOR ANALYSES**

**6.1**

**INTENT-TO-TREAT POPULATION**

The Intent-to-Treat (ITT) Population will consist of all randomized participants who took at least 1 dose of study intervention.

**6.2**

**LOW BASELINE TOTAL T3 SYMPTOMATIC SUBSET OF ITT POPULATION (ITT-T3)**

The low baseline total T3 symptomatic Population (abbreviated as ITT-T3 Population) will consist of all participants in the ITT Population who had a baseline total T3 < 87 ng/dL and a ThyPRO hypothyroidism symptom scale > 0.

**6.3**

**SAFETY POPULATION**

The Safety Population will consist of all participants who took at least 1 dose of study intervention.

**6.4**

**SAFETY-T3 POPULATION**

The Safety-T3 Population will consist of all participants who took at least 1 dose of study intervention and who had a baseline total T3 < 87 ng/dL and a ThyPRO hypothyroidism symptom scale > 0.

## **7.0**

## **PARTICIPANT DISPOSITION**

The number and percentage of participants in the four analysis populations (ITT and ITT-T3 Populations, Safety and Safety-T3 Populations) will be summarized by treatment group and study center; the number of participants screened will be summarized overall only by study center.

Screen-failure participants (i.e., participants who consented to participate in the clinical study but were not randomized) and the associated reasons for failure to randomize will be tabulated for all screened participants.

The number and percentage of participants who complete the double blind treatment period and of participants who prematurely discontinue during the same period will be presented for each treatment group and pooled across treatment groups for the ITT and ITT-T3 Populations. The reasons for premature discontinuation from the double blind treatment period as recorded on the termination pages of the electronic case report forms will be summarized (number and percentage) by treatment group for the ITT and ITT-T3 Populations. All participants who prematurely discontinue during the double-blind period will be listed by discontinuation reason for the ITT and ITT-T3 Populations.

## **8.0**

## **DEMOGRAPHICS AND OTHER BASELINE CHARACTERISTICS**

Demographic parameters (e.g., age, race, ethnicity, sex) and other baseline characteristics (weight, BMI) will be summarized in total and by treatment group for the four analysis populations (ITT and ITT-T3 Populations, Safety and Safety-T3 Populations).

Abnormalities in participants' medical and surgical histories will be coded using the *Medical Dictionary for Regulatory Activities*, version 21.1 or newer. The number and percentage of participants with abnormalities in medical and surgical histories in each system organ class and preferred term will be summarized by treatment group for the ITT and ITT-T3 Populations.

*Prior medication* is defined as any medication started before the date of the first dose of double-blind study treatment. *Concomitant medication* is defined as any medication taken on or after the date of the first dose of double-blind study treatment. Any prior medications started more than 30 days before the date of the first dose of double-blind study treatment and any concomitant medications started after the date of the last dose of double-blind study treatment will not be presented in the summary tables, but will be included in the participant data listings.

Both prior and concomitant medication use will be summarized by the number and proportion of participants in each treatment group for the ITT and ITT-T3 Populations. The *WHO Drug Dictionary*, Version B2 March 2017 or newer, will be used to classify prior and concomitant medications by WHO Drug Anatomical/Therapeutic/Chemical category and drug preferred name. Multiple medications used by a participant will only be counted once for the coded drug preferred name or therapeutic class.

## **9.0**

## **EXTENT OF EXPOSURE AND TREATMENT COMPLIANCE**

### **9.1**

### **EXTENT OF EXPOSURE**

Exposure to the study treatment for the Safety and Safety-T3 Populations during the double-blind treatment period will be summarized for treatment duration, calculated as the number of days from the date of the first dose of double-blind investigational product taken to the date of the last dose taken, inclusive. Descriptive statistics (number of participants, mean, SD, minimum, median, Q1, Q3 and maximum) will be presented by treatment group.

Mean daily dose (by period and overall mean) for the study treatment will be summarized using descriptive statistics (number of patients, mean, SD, median, minimum, Q1, Q3 and maximum). Overall modal daily dose and final daily dose will be summarized by the number and percentage of patients with a pre-specified dose.

[figure not shown]
*Patient-years*, defined as exposure to the study treatment in years, will be summarized by treatment for the Safety and Safety-T3 Populations.

### **9.2**

### **MEASUREMENT OF TREATMENT COMPLIANCE**

*Dosing compliance* for a specified period is defined as the total number of dose-numbers (daily single intervention based on dose level with two capsules, see [Table 9-1](#)) actually taken by a patient during that period divided by the number of dose-numbers that were expected to be taken during the same period multiplied by 100 by treatment group. The total number of dose-numbers actually taken during a specific period is calculated as the number of days in that period multiplied by the number of dose-numbers taken each day during that period. The number of dose-numbers expected to be taken for a specific treatment period will be calculated by multiplying the number of days in that period by the number of dose-numbers to be taken per day.

Descriptive statistics for study drug compliance will be presented by treatment group by period and for the whole double-blind treatment period, for the Safety and Safety-T3 Populations.

## **10.0**

## **EFFICACY ANALYSES**

The efficacy analyses will be performed on the ITT Population or ITT-T3 Population, depending on the endpoints.

### **10.1**

### **PRIMARY EFFICACY ENDPOINT AND ANALYSES**

The primary efficacy endpoint is the achievement of TSH values within the normal reference range of 0.45 to 4.12 mIU/L, inclusive, at both the end of the Titration Period and the end of the Stabilization Period (sustained TSH responder). The primary estimand is the difference in the percentage of sustained TSH responders between the Armour Thyroid and synthetic T4 study intervention groups in the ITT Population. The number and percentage of sustained TSH responders will be summarized by treatment group in the ITT Population. Participants with a missing TSH value at either the end of the Titration Period or at the end of the Stabilization Period will be handled based on Non-Responder Imputation incorporating multiple imputation to handle missing data due to Covid-19 (NRI-C), as outlined later in this section.

The non-inferiority (NI) hypothesis test for the primary efficacy endpoint, based on the ITT Population, will be performed at a 1-sided 2.5% level of significance (equivalent to a two-sided 5% level of significance). The null hypothesis is that Armour Thyroid is inferior to synthetic T4, which will be tested against the alternative hypothesis that Armour Thyroid is non-inferior to synthetic T4, as follows:

$$H_0: p_A - p_T \leq -\Delta \text{ versus } H_a: p_A - p_T > -\Delta$$

Where:  $p_A$  and  $p_T$  are the proportions of TSH responders in the Armour Thyroid and synthetic T4 study intervention groups, respectively; [REDACTED]

The analysis of the primary efficacy endpoint will be performed on the ITT Population using stratum-adjusted Mantel-Haenszel by age group (age < 65 years or  $\geq$  65 years) as described in ([Agresti 2013, p. 231](#)).

The stratified proportion difference is

$$\hat{d}_{MH} = \left( \sum_h \hat{d}_h w_h \right) / \left( \sum_h w_h \right)$$

where  $\hat{d}_h$  is the proportion difference in stratum h and  $w_h = n_{h1} \cdot n_{h2} / n_h$ .

The proportion difference in stratum h is computed as

$$\hat{d}_h = \hat{p}_{h1} - \hat{p}_{h2} = (n_{h11} / n_{h1.}) - (n_{h21} / n_{h2.})$$

where  $\hat{p}_{h1}$  is the proportion of TSH responder for ATH and  $\hat{p}_{h2}$  is the proportion of TSH responder for synthetic T4 at stratum h.

The variance of  $\hat{d}_{MH}$  as

$$\hat{\sigma}^2(\hat{d}_{MH}) = \left( \hat{d}_{MH} \sum_h P_h + \sum_h Q_h \right) / \left( \sum_h w_h \right)^2$$

where

$$P_h = \left( n_{h1.}^2 \cdot n_{h21} - n_{h2.}^2 \cdot n_{h11} + n_{h1.} \cdot n_{h2.} \cdot (n_{h21} - n_{h11}) / 2 \right) / n_h^2$$

$$Q_h = (n_{h11}(n_{h2.} - n_{h21}) + n_{h21}(n_{h1.} - n_{h11})) / 2n_h$$

The  $100(1 - \alpha)\%$  confidence limits for the stratified proportion difference are

$$\hat{d}_{MH} \pm (z_{\alpha/2} \times \hat{\sigma}(\hat{d}_{MH}))$$

[REDACTED]

[REDACTED]

[REDACTED]

The **Non-Responder Imputation** incorporating multiple imputation to handle missing data due to **Covid-19 (NRI-C)** will be performed for participants who have missing TSH values either at the end of the Titration Period or at the end of the Stabilization Period. The NRI-C will categorize any participant who does not have an evaluation at the end of Titration Period or at the end of Stabilization Period as a non-responder. The only exception is that missing data solely due to COVID-19 infection or logistical restrictions related to the COVID-19 pandemic will be handled by Multiple Imputation (MI) under the Missing at Random (MAR) mechanism.

The analysis using NRI-C will be carried out in the following steps.

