9.4.1.2. Primary Analyses

The noninferiority hypothesis test for the primary efficacy parameter, based on the ITT Population, will be performed at a 1-sided 2.5% level of significance. The null hypothesis is that Armour Thyroid is inferior to synthetic T4, which will be tested against the alternative hypothesis that Armour Thyroid is noninferior to synthetic T4, as follows:

$$H_0: rT - rR \leq -\Delta \text{ versus } H_a: rT - rR > -\Delta$$

Where: rT and rR are the proportions of TSH responders in the Armour Thyroid and synthetic T4 study intervention groups, respectively, at the end of the double-blind Stabilization Period; Δ is the noninferiority margin, which is assumed to be 10%.

The primary analysis of the primary efficacy endpoint will be performed on the ITT population based on a stratified method using Mantel-Haenszel (MH) weighted. Within the framework of this method, the difference proportions of sustained TSH responders (Armour Thyroid group minus T4 group) and the corresponding 95% confidence interval for the non-inferiority testing will be computed. Specifically, the confidence intervals for stratified proportion differences will be calculated using the MH-weighted method with the age group (age < 65 years or ≥ 65 years) as a stratification factor as described in Agresti (2013, p. 231). 

A sensitivity analysis of the 2-sided 95% confidence interval for stratified proportion difference will also be performed on the ITT population using stratified Newcombe confidence (Yan 2010).

Sensitivity analyses, based on the ITT population, for participants who are missing TSH values either at the end of the Titration Period or at the end of the Stabilization Period will be provided in detail in the SAP as follows:

- Sustained TSH responder for missing TSH values either at the end of the Titration Period or at the end of the Stabilization Period will be imputed.
- Missing values under an assumption of missing at random will be imputed by multiple imputation approach.
- Tipping-point analysis will be performed to investigate the impact of missing data on the study results.
- The noninferiority between Armour Thyroid and synthetic T4 will be established in the complete-case, which excludes participants who have not completed the study or who are missing TSH values either at the end of the Titration Period or at the end of the Stabilization Period.

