### **4.1**

### **STUDY DESIGN:**

Study 3014-201-002 is a randomized, double-blinded, parallel-group, active-controlled, multicenter, dose-conversion study in previously hypothyroid participants, who are euthyroid on a stable dose of T4 replacement therapy, to evaluate the efficacy and safety of replacement therapy with matching doses of Armour Thyroid in comparison to synthetic T4.

During the coronavirus disease 2019 (COVID-19) pandemic, the mitigation strategy of increasing enrollment has been implemented to overcome the loss of information from the impact of COVID-19. Approximately 284 total participants (an increased enrollment from the original planned sample size of 220 participants specified in the protocol) who meet eligibility criteria will be randomly assigned to study intervention in a 1:1 ratio (approximately 142 participants per arm), stratified by age (< 65 years,  $\geq$  65 years).

The study will last approximately 33 to 51 weeks (with a planned minimum of 7 visits and a maximum of 15 possible visits if participants require additional dose titration) and will include a Screening Period (up to 3 weeks), double-blinded Titration Period (at least 18 weeks), and a double-blinded Stabilization Period (12 weeks).

[figure not shown]
All participants entering the study will be controlled on a stable, FDA-approved, daily dose of synthetic T4 (i.e., euthyroid) for at least 3 months and will be randomized to either the same dose of synthetic T4 or a matching dose of Armour Thyroid during the first visit of the Titration Period (Visit 2). For each available dose of synthetic T4, up to 200  $\mu$ g, a matching dose of Armour Thyroid will be employed according to a dose-conversion table based on the USP Drug Information 2000. Armour Thyroid and synthetic T4 will be administered as a single oral dose of 2 capsules (one of these capsules may be placebo), once-daily, on an empty stomach at least 30 to 60 minutes before the first meal. Serum TSH levels will be measured prior to study intervention administration during study visits.

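### The Mantel-Haenszel variance printed in SAP 10.1 has responder counts where arm sizes belong in P_h, so it does not reduce to the binomial variance; the effect is small and a one-line correction is enough

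*SAP*

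**What the plan says.** SAP 10.1 analyses the primary endpoint "using stratum-adjusted Mantel-Haenszel by age group", citing a textbook page, and then writes the calculation out.

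- **Notation.** The stratum difference is built from "n_{h11} / n_{h1.}) - (n_{h21} / n_{h2" and its closing marks. So n_h11 and n_h21 are responders, and n_h1. and n_h2. are arm sizes, for Armour Thyroid and synthetic T4 respectively.
- **Variance.** It is assembled as "d}_{MH} \sum_h P_h + \sum_h Q_h \right) / \left( \sum_h w_h \right)^2".
- **P_h.** The numerator, divided by n_h^2, ends in "n_{h1.} \cdot n_{h2.} \cdot (n_{h21} - n_{h11}) / 2".
- **Q_h.** "Q_h = (n_{h11}(n_{h2.} - n_{h21}) + n_{h21}(n_{h1.} - n_{h11})) / 2n_h".

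The interval is d_MH plus or minus z times the square root of this variance. It carries the non-inferiority test, which "will be performed at a 1-sided 2.5% level of significance". The margin is blacked out in the SAP. Protocol 9.4.1.2 gives it: Δ "is the noninferiority margin, which is assumed to be 10" per cent.

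SAP 10.1 (Steps 2 and 3) applies the method to each of 100 imputed datasets and pools the results. SAP 10.2 uses it for the secondary endpoint. SAP 15.0 names SAS 9.4 or newer, but no procedure or option is named for this interval.

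**The concern.** The third part of P_h is there to handle unequal arm sizes and should vanish when the arms are equal. As printed, it is a difference of responder counts, so it vanishes only when those counts happen to agree. The result then no longer equals the ordinary binomial variance in the simplest case.

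At stake is whether the written definition of the primary interval can be reproduced. A programmer who codes the SAP text and a validator who uses a formula that does reduce to the binomial variance would get different standard errors for the primary and secondary results.

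**Working it through.** The documents give no standard error, interval or response rate for this analysis, and the sample-size section is blacked out. There is no stated figure to reproduce, so the formula is tested against properties it must have.

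**Inputs.** Formula and notation: SAP 10.1. Size: SAP 4.1, "in a 1:1 ratio (approximately 142 participants per arm". Margin: 10 points (protocol 9.4.1.2). z = 1.96. Synthetic T4 response pT of 70-90% is my assumption.

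**Check 1: one stratum, n per arm.** Here n_h = 2n, w = n/2 and d = p1 - p2.

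- Arm-size term: it is zero, so P = (x2 - x1)/4 = -nd/4, where x1 and x2 are responders.
- Q = n(p1q2 + p2q1)/4.
- Variance = (dP + Q)/w^2 = (p1q2 + p2q1 - d^2)/n = (p1q1 + p2q2)/n, the binomial variance.
- Printed term: it adds (x2 - x1)/8 = -nd/8 to P. The variance becomes (p1q1 + p2q2)/n - d^2/(2n).

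Example, 0.75 v 0.85 with 142 per arm:

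- Binomial: (0.1875 + 0.1275)/142 = 0.0022183, SE 0.04710.
- Shortfall: 0.01/284 = 0.0000352.
- Printed: 0.0021831, SE 0.04672.

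**Check 2: swapping responder and non-responder.** This must leave the variance unchanged. With 150 v 134 at 0.75 v 0.85, the printed form gives 0.002158 one way and 0.002198 the other. The arm-size form gives 0.002201 both ways, which is the binomial value: 0.1875/150 + 0.1275/134.

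**Direction.** Write y1 and y2 for non-responders. In one stratum, printed minus correct variance is d(y1 - y2)/(2 n1 n2). With several strata, each contributes with the sign of d_MH(y_h1 - y_h2). With equal arms in a stratum, y_h1 - y_h2 = -n d_h, where n is the stratum's per-arm size. If the strata share a direction, every contribution is negative and the SE is too small. With unequal arms the sign can reverse:

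- 138 v 146 at 79% v 80%: y1 - y2 = 28.98 - 29.20 = -0.22 and d = -0.01, so the product is positive. SE 0.047939 printed, 0.047938 correct.
- 132 v 152 at 78% v 80%: y1 - y2 = 29.04 - 30.40 = -1.36 and d = -0.02. SE 0.048511 printed, 0.048504 correct.

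**Size at 142 per arm, one stratum.**

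| pT | d | SE correct | SE printed | shortfall | lower limit, correct | lower limit, printed |
|---|---|---|---|---|---|---|
| 0.70 | -0.05 | 0.05551 | 0.05543 | 0.14% | -0.1588 | -0.1586 |
| 0.70 | -0.10 | 0.05629 | 0.05598 | 0.56% | -0.2103 | -0.2097 |
| 0.80 | -0.05 | 0.04947 | 0.04938 | 0.18% | -0.1470 | -0.1468 |
| 0.80 | -0.10 | 0.05105 | 0.05070 | 0.68% | -0.2000 | -0.1994 |
| 0.90 | -0.05 | 0.03914 | 0.03902 | 0.29% | -0.1267 | -0.1265 |
| 0.90 | -0.10 | 0.04196 | 0.04154 | 1.01% | -0.1822 | -0.1814 |

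At d = 0 the two forms agree in this balanced case. At pT = 0.95 and d = -0.10 the shortfall is about 1.4%.

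**Decision.** I simulated 200,000 trials per scenario with two age strata (assumed about 114 and 28 per arm, each cell varying by up to 2).

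- The printed SE was too small in 95-99.8% of trials and too large in 0.1-2.9%. The mean ratio of printed to correct SE was 0.988-0.998.
- At a true difference of -0.10, non-inferiority was declared at these rates (printed v correct): 0.0252 v 0.0251 (pT 0.70), 0.0256 v 0.0256 (0.80) and 0.0274 v 0.0274 (0.90).
- Across all scenarios the two forms disagreed on the decision in at most 0.07% of trials.

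**The case against.** **It may be a misread PDF.** The whole point turns on subscripts: n_h2. against n_h21, and n_h1. against n_h11. The text was machine-read, and the weight w_h in the same section has lost its marginal dots. This is possible but unlikely. Both subscripts in one bracket would have to change in the same way, while the dots on the four other arm-size terms of P_h and on those in Q_h survived. It does justify looking at the original first.

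**The method is cited and standard software exists.** True, and nothing says the expression will be hand-coded. A reader might infer that the trial's programmed standard error is wrong; no document shows what was coded, so that does not follow. But the citation does not cure a formula the SAP prints, since no SAS procedure is named for the interval. The stratified Newcombe interval is planned only alongside three sensitivity analyses.

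**The consequence is negligible.** Largely right. In the 0.75 v 0.85 example the limits are -19.23% to -0.77% (correct) and -19.16% to -0.84% (printed), which are the same to one decimal. Running 100 imputations does not multiply the error, because pooling averages the within-imputation variances. This objection sets the grade of the point; it does not make the formula right.

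**Conclusion.** The variance is wrong as printed. This follows from the SAP's own definitions by algebra, subject only to confirming the subscripts in the original PDF. For |d| of 0.05-0.10 the effect is about 0.2-1% of the standard error (0.14% at the mildest corner of the table), assuming 70-90% response and 142 per arm. It is practically nil for the non-inferiority decision. It is a minor correction that concerns the accuracy and reproducibility of the primary and secondary intervals.

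A reader might infer that the standard error is too small whenever the difference is not zero. The formula does not support that: the direction is assured for balanced arms with a common direction across strata, and unequal arms can make the error zero or slightly positive. The SAP promises only approximately equal arms, so exact balance within age strata cannot be taken for granted.

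**What to change.** Check P_h in the original PDF of SAP 10.1. If the subscripts are as read here, replace (n_h21 - n_h11)/2 by (n_h2. - n_h1.)/2 in its last part. Alternatively, delete the written-out variance and name the validated SAS procedure and option that will produce the Mantel-Haenszel risk-difference interval. Section 10.2 refers back to 10.1 and needs no separate change. The cost is one line of SAP text, with no effect on design, sample size or data collection.

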### **Step 1. Imputation**

**Step 1.1 Multiple imputation for TSH values:** 100 imputed datasets of TSH values at the end of Titration Period and the end of Stabilization Period will be generated using SAS PROC MI FCS REG. The random seed 12345 will be used. The following covariates will be included in the imputation model:

- 1) Randomized treatment group
- 2) Stratification group (age  $< 65$  years or  $\geq 65$  years)
- 3) Baseline TSH
- 4) TSH at the end of Titration Period for the imputation of missing TSH at the end of Stabilization Period

**Step 1.2. Imputing Responder Status:** In the imputed datasets from Step 1.1, the responder status (yes/no) will be derived from the TSH values at the end of Titration

Period and the end of Stabilization Period according to the normal reference range (0.45-4.12 mIU/L, inclusive) based on the imputed values with the following exception:

The participants who have missing TSH values either at the end of the Titration Period or at the end of the Stabilization Period for reasons other than solely due to COVID-19 infection or logistical restrictions related to the COVID-19 pandemic, the non-responder status will be assigned to these participants in the imputed datasets regardless of the imputed values.

**Step 2. Analysis:** Each of the 100 imputed datasets from Step 1.2 will be analyzed separately using the above mentioned stratified Mantel-Haenszel test.

**Step 3. Pooling:** The point estimate and 95% confidence interval of the stratified proportion difference from the 100 imputed datasets are combined into one overall result using **PROC MIANALYZE**.

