**Figure 4-1**      **3014-201-002 Study Schematic**

\* If a participant undergoes up to the maximum of 3 additional dose titrations starting at Week 18, the Titration Period may extend up to Week 36; therefore, the Stabilization Period may extend from Week 36 to Week 48 (remaining 12 weeks in duration). The Primary Endpoint will be measured at the end of the Titration Period and the end of the Stabilization Period.

During the Titration Period, study visits are split into parts A and B (i.e., Visit 3a, Visit 3b, Visit 4a, Visit 4b) to allow for any dose titrations:

- Visits 3a and 4a are mandatory for all participants. Study assessments, including bloodwork for total T3, TSH, and study intervention dispensing will be performed.
- Visits 3b and 4b are only required for participants needing a dose titration based on the data obtained from Visits 3a and 4a, respectively. A limited number of assessments and study intervention dispensing will be performed.

Visit 5 is designed as a transition visit between the Titration and Stabilization Periods and may consist of a subset of visits (starting with Visit 5a [Week 18] and extending to Visit 5g [Week 36], as needed). The last visit within Visit 5 serves as both the end of the Titration Period and the beginning of the Stabilization Period.

- Participants with TSH levels within normal reference range at Visit 5a may enter the Stabilization Period (i.e., their next visit will be Visit 6).
- If participants' TSH levels are out of normal reference range at Visit 5a, participants' doses can be up- or down-titrated per the Investigators' interpretation until their TSH levels are within the normal reference range by continuing the Titration Period

beyond Week 18. If the Titration Period is continued, the participants' doses can be up- or down-titrated approximately every 6 weeks until their TSH levels have normalized for up to a maximum of 3 additional titrations (including the titration at Visit 5b). Once their TSH levels are within the normal reference range, participants can enter the Stabilization Period. Participants whose TSH levels have not normalized after the maximum of 3 additional titrations will not enter the Stabilization Period.

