### **NRI incorporating Multiple Imputation (NRI-MI)**

The Non-Responder Imputation incorporating Multiple Imputation (NRI-MI) will be carried out for all the missing TSH values in the steps similar to the ones described above for NRI-C, with the exception of Step 1.2.

**Step 1.2. Imputing Responder Status:** In the imputed datasets from Step 1.1, the responder status (yes/no) will be derived from the TSH values at the end of Titration Period and the end of Stabilization Period according to the normal reference range (0.45-4.12 mIU/L, inclusive) based on the imputed values with the following exception: For participants who prematurely discontinue from the study due to lack of efficacy, adverse events related to study drug, or death, the non-responder status will be assigned to these participants in the imputed datasets regardless of the imputed values.

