### **Multiple Imputation**

The Multiple Imputation (MI) analysis will be carried out for all the missing TSH values regardless of reasons for missingness in the steps similar to the ones described above for NRI-C, with the exception of Step 1.2.

**Step 1.2. Imputing Responder Status:** In the imputed datasets from Step 1.1, the responder status (yes/no) will be derived from the TSH values at the end of Titration Period and the end of Stabilization Period according to the normal reference range based on the imputed values.

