## 10.2

## SECONDARY EFFICACY ENDPOINTS

### **The Achievement of Titration TSH Response**

The achievement of titration TSH Response is defined as TSH values that are within the normal reference range of 0.45 to 4.12 mIU/L, inclusive, at the end of the Titration Period (Titration TSH Responder). The secondary estimand is the difference in the percentage of Titration TSH Responders between the Armour Thyroid and synthetic T4 study intervention groups in the ITT population. The number and percentage of titration TSH responders will be summarized by treatment group in the ITT Population along with the 2-sided 95% CI for the stratified proportion difference. The non-inferiority (NI) hypothesis test for the secondary efficacy endpoint, based on the ITT Population, will be performed at a 1-sided 2.5% level of significance (equivalent to a two-sided 5% level of significance). The analysis of the secondary efficacy endpoint will be performed on the ITT Population using stratum-adjusted Mantel-Haenszel by age group (age < 65 years or  $\geq$  65 years) as described in the Section 10.1 (Agresti 2013, p. 231).

The **Non-Responder Imputation** incorporating multiple imputation to handle missing data due to Covid-19 (NRI-C) will be performed for participants who have missing TSH values at the end of the Titration Period similar to the primary efficacy analysis outlined in Section 10.1.

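### Step 1.1 imputes TSH by untransformed normal regression with one residual variance for both arms, so it can draw negative TSH values that are scored as non-response

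*SAP*

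**What the plan says.** Under SAP 10.1 (NRI-C), a participant lacking TSH at the end of titration or the end of stabilization is a non-responder unless the value is missing solely for COVID-19 reasons; those values are multiply imputed. Step 1.1 states that 100 datasets "will be generated using SAS PROC MI FCS REG. The random seed 12345 will be used". The covariates are "Randomized treatment group", age group, baseline TSH and "4) TSH at the end of Titration Period for the imputation of missing TSH at the end of Stabilization Period". Step 1.2 then scores every imputed value against 0.45–4.12 mIU/L.

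The same model is used elsewhere:

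- The secondary endpoint (SAP 10.2) handles "missing TSH values at the end of the Titration Period similar to the primary efficacy analysis outlined in Section 10.1".
- The NRI-MI sensitivity analysis "will be carried out for all the missing TSH values in the steps similar to the ones described above for NRI-C", with only Step 1.2 changed.
- The MI sensitivity analysis "will be carried out for all the missing TSH values regardless of reasons for missingness", again with only Step 1.2 changed.

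Two design features in SAP 4.1 matter. Titration is a stopped process: "Once their TSH levels are within the normal reference range, participants can enter the Stabilization Period". And participants "will be randomized to either the same dose of synthetic T4 or a matching dose of Armour Thyroid during the first visit", so only the Armour arm changes product.

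**The concern.** FCS REG draws each missing value from a normal distribution around a linear predictor, with one residual variance. On raw TSH nothing prevents draws below zero. Because the endpoint is a threshold on the imputed value, a wrong distributional shape becomes a wrong response rate.

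Two further problems are specific to this trial. Observed end-of-titration values are mostly confined to the reference range by the stopping rule, and a normal fit spills outside that range even on the log scale. Treatment as a covariate shifts the mean only. If TSH is more variable on Armour, the pooled variance makes Armour look too stable and T4 too unstable among imputed participants, which pulls the arms together. In a non-inferiority trial that is the favourable direction. NRI-MI and MI share the model, so they cannot expose the problem.

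**Working it through.** **Inputs from the documents.** Margin 10 points (Protocol 9.4.1.2), one-sided 2.5% (SAP 10.1), about 142 per arm (SAP 4.1), range 0.45–4.12 mIU/L. **Assumptions.** Log-normal TSH, between-visit correlation 0.5, and the medians, log-SDs and missing rates shown. The plan gives no figure on this point to reproduce.

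**1. Closed form.** For log-normal TSH with median m and log-SD s, the mean is μ = m·exp(s²/2) and the SD is σ = μ·√(exp(s²) − 1). A normal with that mean and SD has P(TSH < 0) = Φ(−1/√(exp(s²) − 1)), whatever m is. At s = 0.6, √(exp(0.36) − 1) = 0.658 and Φ(−1.519) = 6.4%. With m = 1.5, μ = 1.796 and σ = 1.182, so the in-range probability at one visit is Φ(1.966) − Φ(−1.138) = 0.848. The true value is Φ(1.684) − Φ(−2.007) = 0.932.

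| log-SD | Below zero | In range, normal | In range, true |
|---|---|---|---|
| 0.4 | 0.8% | 0.959 | 0.993 |
| 0.6 | 6.4% | 0.848 | 0.932 |
| 0.8 | 14.5% | 0.649 | 0.831 |
| 1.0 | 22.3% | 0.428 | 0.730 |

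**2. Simulation A, following the design.** Screening TSH is in range. There are up to four end-of-titration looks, stopping at the first in-range value, with the set point moved halfway to the median after each out-of-range look. Visit 7 is missing at random. Imputation uses Bayesian regression draws with the SAP predictors except age group. Response among imputed participants:

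| Median, log-SD | Negative draws | Raw (SAP) | Log | True |
|---|---|---|---|---|
| 1.5, 0.5 | 2.3% | 92.3% | 97.4% | 97.7% |
| 1.8, 0.6 | 4.5% | 86.5% | 93.1% | 93.7% |
| 1.8, 0.7 | 7.3% | 79.6% | 89.9% | 90.3% |

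A repeat under the same assumptions gave 2.3%, 4.6% and 7.5% negative draws, and raw 92.4%, 86.4% and 79.6% against true 97.8%, 93.3% and 90.4%.

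**3. Effect on the arm difference, equal spread.** With missing fractions f_A and f_T, the bias is about (imputed − true response) × (f_A − f_T). At 15% Armour and 5% T4:

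- log-SD 0.5: (92.3 − 97.7) × 0.10 = −0.5 points
- log-SD 0.6: (86.5 − 93.7) × 0.10 = −0.7
- log-SD 0.7: (79.6 − 90.3) × 0.10 = −1.1

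The simulated biases are the same, and the signs reverse when the split is mirrored. At 10% in each arm the bias is 0.0 to 0.1. The chance of showing non-inferiority with equal arms and 10% missing each, raw against log, is 99.7% v 99.7%, 89.3% v 91.6% and 74.7% v 79.4%.

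**4. Unequal spread.** In simulation A, with log-SD 0.8 Armour and 0.5 T4 (true difference about −9.6), the bias toward non-inferiority is +0.9 points for both raw and pooled log at 10% missing each, and +1.2 to +1.3 at 15%. Imputing within arm gives 0.0 and −0.05.

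Simulation B has no titration stopping, lets half of those missing the last value also miss end of titration, and uses the SAP's Mantel-Haenszel variance with Rubin pooling. Armour log-SD was set at 0.643 against 0.50, so that the true difference is exactly −10. Estimated difference in points, with the rate of declaring non-inferiority in brackets (Monte Carlo SE about 0.006):

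| Missing per arm | Full data | Raw (SAP) | Pooled log | Log by arm |
|---|---|---|---|---|
| 5% | −9.9 (0.038) | −9.5 (0.035) | −9.6 (0.041) | −10.0 (0.035) |
| 10% | −10.2 (0.029) | −9.2 (0.028) | −9.5 (0.030) | −10.2 (0.024) |
| 20% | −10.2 (0.030) | −8.3 (0.026) | −8.8 (0.039) | −10.3 (0.025) |

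With equal arms in B (log-SD 0.5, 20% missing), the chance of showing non-inferiority is 0.89 raw, 0.94 pooled log, 0.92 log by arm and 0.95 with full data.

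**5. Missing end of titration.** In simulation A the true in-range rate is about 100%. The raw model imputes 93–95%, log 96–98% and predictive mean matching 100%. Adding Visit 6 as a predictor changed mean imputed response by 0.1 point or less.

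**The case against.** **Size is assumed, and the simulations disagree on it.** This stands. At median 1.5 and log-SD 0.5, A gives 2.3% negative draws while B gives about 4%, with imputed response 0.87 against a true 0.945. They agree in direction. That response is understated rests on TSH being right-skewed.

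**Few participants are affected in the primary analysis.** Only values missing solely for COVID-19 reasons keep their imputations, and such missingness should be largely unrelated to blinded arm. If independent of arm at 10%, the difference in missing fraction has SD √(2 × 0.1 × 0.9/142) = 3.6 points, so a 15%/5% split is about 2.8 SD. A one-SD imbalance gives a bias of only about 0.2 to 0.4 points. This stands.

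**Unequal spread has no support in the documents.** Both arms are titrated to the same range, and Protocol 2.2 reports that all patients in the earlier crossover study remained within acceptable TSH range. Wider Armour spread is indeed only a possibility. But nothing assures equal spread either, and imputing within arm removes the need to assume it.

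**No visible type I inflation for the raw model.** Simulation B supports this. Correcting the scale alone is less reassuring. In a separate run at log-SD 0.8 v 0.5 with 15% missing, non-inferiority was declared at a rate of 0.088 with pooled log and 0.034 with log by arm. The true difference in that setting is about −9.6, so it lies close to the margin but not on it.

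**Other safeguards.** Non-responder, responder, complete-case and tipping-point analyses avoid the model. End-of-titration values should seldom be missing, because SAP 16.2 ends titration at the last TSH visit before Visit 6. Redacted text before the NRI-C description and in SAP 17–18 could mention a transformation; Step 1.1 itself is not redacted. All of this limits the consequence without correcting the model.

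**Conclusion.** The concern holds on the visible text. Followed literally, Step 1.1 can produce impossible TSH values, and Step 1.2 scores them as failures in the primary, secondary, NRI-MI and MI analyses.

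Under the stated assumptions, response among imputed participants is understated by about 5 to 11 points in the design-based simulation. With balanced missingness and equal spread, the arm difference is almost unbiased and the loss is 0 to about 5 points of power at 10% missing. With wider Armour spread, the estimate moves toward non-inferiority by about half a point at 5% missing and about 2 points at 20%, against a 10-point margin. No inflation of false non-inferiority was seen for the raw model.

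The flaw in the method is certain and its size in this trial is not. It should be fixed before unblinding, but it does not by itself undermine the primary conclusion.

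**What to change.** In Step 1.1:

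- Impute separately within each treatment arm.
- Use predictive mean matching on log TSH, or impute log TSH and back-transform before applying 0.45–4.12. Prefer matching for end-of-titration TSH, whose observed values are stopped in range. A log transform alone removes negative draws but leaves the shared variance.
- Optionally, add log TSH at Visits 3a and 4a for end of titration, and at Visit 6 for end of stabilization. The gain is small. These values can be missing too, so they must be in the same imputation chain.
- Carry the model into SAP 10.2, NRI-MI and MI. If a redacted passage already states a transformation, cite it in Step 1.1.

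The cost is a few lines of SAP text and code, with no new data. Imputing within arm gives up about 1 point of power against pooled log (at log-SD 0.6 and 10% missing: 91.6% pooled log, 90.7% log by arm, 90.1% matching by arm), because each arm's model has fewer observations. Both within-arm options are still no worse than the plan as written, at 89.3%.
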